6.5 Pharmacokinetic Measures

Table 5. PK and PK/PD Endpoint

	Endpoint
Secondary PK and PK/PD	
● TBA-7371 concentration profiles and PK parameters over the 14-day treatment interval: C_{max}, T_{max}, C_{last}, T_{last}, AUC_{inf}, AUC_{last}, AUC_{tau}, C_{min}, half-life, accumulation ratios.● Correlation between TBA-7371 AUC, C_{max}, T>MIC and CFU counts on solid media culture.● Expected concentration associated with 90% of the maximal TBA-7371 EBA effect (EC90).

7 STUDY POPULATIONS

7.1 Populations for Analyses

Analysis populations are show in Table 6.

Table 6. Populations for Analyses

Population	Description
Randomized population	All participants randomly assigned to study intervention, who either have randomized date or randomization number.
Modified intention to treat (mITT) efficacy population	All participants randomly assigned to study intervention, who received at least one dose of the study intervention. Participants will be analyzed according to the intervention they actually received.
Per Protocol (PP) efficacy population	All participants randomly assigned to study intervention, who received the study intervention, and did not substantially deviate from the protocol procedures. Participants who substantially deviated will be identified prior to database lock. Participants will be analyzed according to the intervention they actually received.
Safety population	All participants randomly assigned to study intervention and who received at least one dose of the study intervention. Participants will be analyzed according to the intervention they actually received.
PK population	All participants who received at least one dose of TBA-7371 and have at least one pair of pre- and post-dose blood samples with measurable concentrations.

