9.3. Populations for Analyses

Analysis populations are shown in Table 8.

Table 8 Populations for Analyses

Population	Description
Modified intention to treat (mITT) efficacy population	All participants randomly assigned to study intervention, who received the study intervention. Participants will be analyzed according to the intervention they actually received.
Per Protocol (PP) efficacy population	All participants randomly assigned to study intervention, who received the study intervention, and did not substantially deviate from the protocol procedures. Participants who substantially deviated will be identified prior to database lock and unmasking. Participants will be analyzed according to the intervention they actually received.
Safety	All participants randomly assigned to study intervention and who received the study intervention. Participants will be analyzed according to the intervention they actually received.
PK population	All participants who received at least one dose of TBA7371 and have at one blood sample with measurable concentrations

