8 CHANGES IN CONDUCT / RE-LANNED ANALYSES FROM THE PROTOCOL

No changes have been made to the planned analyses.

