12. **Overnight sputum collection for EBA assessment and exploratory measurements.** Overnight[†] sputum will be collected from 3 PM to 7 AM of the following Day (16 hours) on Days -2 and -1 during Screening Phase and on 14 consecutive Days during the Study Treatment Phase (Days 1 to 14) for EBA assessment. The last collection will finish at 7 AM of Day 15. [†]Ability to sting for isoniazid and rifampicin, and minimum inhibitory concentrations (MIC) of TBA-7371 will be performed on either of Day -2 or Day -1 and again on Day 14.

13

14. Recording of AE, SAE (including serious ADR) and AESI; recording of concomitant treatments. Adverse events (AE), serious adverse events (SAE), including serious adverse drug reactions (ADR), adverse events of special interest (AESI) and concomitant treatments will be recorded from the time each participant has signed the informed consent form (ICF) until he/she has completed the last follow-up visit (Day 42) or the Early Withdrawal Visit (EWV).

15. **Blood/serum sample collection for PK measurements.** WILL BE CONDUCTED ONLY IN PARTICIPANTS RANDOMIZED TO TBA-7371. Timing of sampling will be as follows:

- Study Treatment Phase: Days 1, 2, 4, 7 and 14 before administration of the 1st daily dose of study drug; in addition, on Days 1, 7 and 14 samples will also collected 30 min (+/- 5 min) and at 1h, 2.5h, 3h, 4h, 6h, 7h, 10.5h, 12h, 16.5h (+/- 15 min) after 1st daily dose of study drug. (see Table 4 of the protocol). Patients assigned to BID dosing will not have collections at 16.5h, and the 12h sample will be taken prior to the second daily dose. Patients assigned to TID dosing will not have collections at 10.5h, 12h and 16.5h, and the 7h sample will be taken prior to the second daily dose.

When timing coincides, samples must always be taken after recording of ECG and vital signs.

16

Coronavirus Disease (COVID-19) / Severe Acute Respiratory Syndrome Coronavirus 2 (SARS-CoV-2 Testing). COVID-19 testing will be conducted via PCR using a test product authorized by SAHPRA at an accredited public or private sector laboratory. A specimen will be collected during the screening period between Day-7 to Day -3, and a negative result must be confirmed prior to randomization. For safety monitoring purposes, testing will also be performed at Day 7 (± 2 Days), on Day 14 OR Day 15 before discharge, and/or at any other time that infection is suspected.

Approved

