Appendix 5 Document History

DOCUMENT HISTORY	
Document	Date
Original SAP	22 Nov 2019
Amendment 1	23 Aug 2021
Amendment 2	27 June 2022

Changes in Amendment 1:

Modifications were made to the following sections of the SAP:

Section 4.0 Introduction

- Revise text with respect to the protocol amendment

Section 5.2 Objectives and Endpoint

- Revise text with respect to the protocol amendment

Section 6 Study Design Considerations

- Revise text with respect to the protocol amendment

Section 7 Study Population

- Remove completer population

Section 9 Overall Statistical Considerations

- Define baseline values of vital signs

Section 10 Statistical Analysis Methods

- Add drug susceptibilities and MIC of TBA-7371 to summary of baseline characteristics

Section 11

- Add description for computing CFU/mL

Section 12 Safety Analyses

- Clarify determination of AEs of special interest per Investigator discretion
- Add line plots of mean of intraday and daily heart rate, SBP, and DBP in supine and standing position
- Add line plots of mean of orthostatic change in intraday and daily heart rate, SBP, and DBP
- Add boxplots of intraday and daily values of QTcF
- Revise analyses for eye symptoms, visual acuity, and color vision test

- Add summary of COVID-19/SARS-CoV-2 test
- Add summary of drug susceptibilities and MIC of TBA-7371

Section 16 References

- Update references

Changes in Amendment 2:

Modifications were made to the following sections of the SAP:

Section 2 Signature Page

- Author of SAP changed from [REDACTED] to [REDACTED]
- Approval changed from [REDACTED] to [REDACTED]

Section 7.1 Population for Analyses

- Randomized population definition added.
- Clarity added for the timing of PK samples to the PK population definition.

Section 11.1.1 Primary Analysis

- Clarity added for starting values for the bilinear regression model
- Clarity added regarding equations, refined definition of BACfu(0-14) for bilinear model
- Clarity added to use of PROC NLMIXED for both linear and bilinear models

Section 11.1.2 Secondary Analysis

- Clarity added to bilinear models used for secondary analysis.

Section 11.1.3 Sensitivity Analysis

- Updated the use of Bayesian model to ANCOVA using averaged change from baseline, as well as a mixed model

Section 11.3 Subgroups

- Added HIV status at Baseline as a subgroup.

Section 13.2 Pharmacokinetic analyses

- Clarity added regarding models and statistics used for reporting

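### The SAP's PK population needs a measurable pre- and post-dose pair, which is stricter than the protocol's one measurable sample, can exclude QD participants with valid Day 1 profiles, and is not declared as a change

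*SAP*

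**What the plan says.** Protocol section 9.3, Table 8, defines the PK population as "All participants who received at least one dose of TBA7371 and have at one blood sample with measurable concentrations" (a word such as 'least' is evidently missing). SAP section 7.1, Table 6, keeps the one-dose condition but requires that participants have "at least one pair of pre- and post-dose blood samples with measurable concentrations".

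SAP section 8 states: "No changes have been made to the planned analyses". The SAP document history (Appendix 5, Amendment 2) records the edit as "Clarity added for the timing of PK samples to the PK population definition".

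The sampling schedule in SAP Appendix 1 puts pre-dose samples on "Days 1, 2, 4, 7 and 14 before administration of the 1st daily dose of study drug". It adds that "on Days 1, 7 and 14 samples will also collected 30 min" after the first daily dose and at further times that day. On those three profile days the BID 12h sample and the TID 7h sample are drawn just before the second dose.

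Four other SAP provisions bear on the point:
- The AUC definitions in section 13.1 treat a measurable concentration as one at or above the LLOQ.
- Section 13.1 sets values below the quantification limit to zero and plans Day 1, 7 and 14 parameters.
- Section 13 runs all PK and PK/PD analyses in the PK population.
- Section 13.3 limits the EC90 fit to members of that population with Day 14 PK data.

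**The concern.** A population definition decides who is counted before any parameter is computed. Here the SAP replaces a condition that almost any sampled participant meets with one that depends on having drug on board before a dose. That cannot be so before the first dose on Day 1. A participant can therefore supply a usable Day 1 profile and still be outside every PK and PK/PD analysis.

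Three things are at stake. First, valid data may be discarded, including data from people who stop early, for whom the protocol added a PK sample at the Early Withdrawal Visit (Table 4; rationale in Appendix 7). Second, membership depends in part on the measured concentration, and it may differ by schedule in a trial that sets out to compare fractionated with QD dosing (Protocol section 4.3). Third, the SAP and protocol disagree while the SAP says they do not.

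**Working it through.** The documents give no size or exclusion rate for the PK population, so there is no planned figure to reproduce. The check compares each rule with the sampling schedule and then sizes the trough risk under assumptions.

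**Step 1. When can a QD participant first qualify?** Pre-dose days are 1, 2, 4, 7 and 14. Post-dose days are 1, 7 and 14. The Day 1 pre-dose sample is drug-free, so same-day pairs with drug already on board exist only on Days 7 and 14. If a pre-dose sample may be paired with a post-dose sample from another day, the earliest pair is the Day 2 pre-dose sample with any Day 1 post-dose sample.

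| Last day with a sample (QD) | Protocol Table 8 | SAP, pair must be same-day | SAP, pair may span days |
|---|---|---|---|
| Day 1 | in | out | out |
| Days 2 to 6 | in | out | in, if a trough is measurable |
| Day 7 onward | in | in, if a Day 7 or 14 trough is measurable | in, if any trough is measurable |

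The protocol column assumes at least one measurable Day 1 sample. SAP section 13.1 schedules ten Day 1 post-dose samples for QD, nine for BID and seven for TID.

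**Step 2. BID and TID.** On Day 1 the 12h (BID) or 7h (TID) sample precedes the second dose and follows the first, so drug can be measurable. No sample is scheduled after the second dose that day. These participants therefore qualify on Day 1 only if that sample counts as pre-dose and may be paired with an earlier post-dose sample. The SAP settles neither question. QD participants have no such route.

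**Step 3. Troughs below the limit.** Neither the LLOQ nor the half-life is in the documents. Assume first-order decline and a peak about 2 h after dosing, so trough/peak = 2^(-t/half-life). The time t is 24 - 2 = 22 h for QD and 12 - 2 = 10 h for BID. For TID it is (24 - 14) - 2 = 8 h, across the overnight gap after the 14h dose.

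| Assumed half-life (h) | QD trough, % of peak | BID | TID |
|---|---|---|---|
| 2 | 0.05 | 3.1 | 6.3 |
| 3 | 0.6 | 9.9 | 15.7 |
| 4 | 2.2 | 17.7 | 25.0 |
| 6 | 7.9 | 31.5 | 39.7 |
| 8 | 14.9 | 42.0 | 50.0 |
| 12 | 28.1 | 56.1 | 63.0 |

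Solving for the half-life below which a QD trough is under the limit:
- LLOQ at 1% of peak: 22 / log2(100) = 22 / 6.644 = 3.3 h.
- LLOQ at 0.5% of peak: 22 / log2(200) = 2.9 h.
- LLOQ at 0.1% of peak: 22 / log2(1000) = 2.2 h.

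Under the pair-may-span-days reading, a QD participant with samples throughout is lost only if the pre-dose values on Days 2, 4, 7 and 14 are all below the limit. Under the same-day reading, it is enough that Days 7 and 14 are.

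**Step 4. Size per participant.** Each TBA-7371 group has 15 participants, so one lost is 1/15 = 6.7% and two are 2/15 = 13.3%. The first two treatment-phase drop-outs per cohort are not replaced.

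**Step 5. Which analyses are touched.** Early withdrawals have no Day 14 data, so section 13.3 leaves them out of the EC90 fit under either definition. For them the effect is on the concentration summaries, the Day 1 and Day 7 parameters and the section 13.2 correlations. A participant with a full Day 14 profile but every trough below the limit is different. That person has a valid Day 14 Cmax, the exposure measure in the EC90 model, and would still be removed from the fit.

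**The case against.** The strongest reply is that this is a wording matter with little practical reach. Protocol section 9.4 leaves the SAP to describe the analysis populations further, and the edit is logged in Appendix 5. Values below the limit are set to zero and not discarded, which suggests the author wanted samples around a dose and did not mean to exclude low troughs. Protocol section 7.2 expects withdrawal to be uncommon. Only secondary analyses use this population.

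Much of this is fair, and it limits the consequences. It does not remove the inconsistency. The log entry calls the edit a clarification although it can remove participants, and section 8 still denies any change. The lenient reading is possible, but section 13.1 ties measurable to the LLOQ and nothing tells a programmer to waive that for the pre-dose member of the pair. Early stopping is also foreseeable: a positive COVID-19 test ends treatment, and the Day 7 test window opens on Day 5.

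Three stronger readings are tempting, and the documents do not support them:
- A reader might infer that nobody can have a measurable pre-dose sample on Day 1. That is true of the first daily dose only; BID and TID have a later pre-dose sample that day.
- A reader might infer that everyone stopping before Day 7 is lost. That needs a same-day requirement the SAP does not state.
- A reader might infer that QD exposure and the exposure-response fit are biased upward. Without an LLOQ or half-life, it cannot be determined whether low troughs drop anyone. Selecting on exposure also does not by itself bias a correctly specified model of response on exposure; it costs range and precision.

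**Conclusion.** The SAP definition is wrong as written. It is stricter than the protocol's, and SAP section 8 does not declare the difference. Read literally, it excludes any QD participant whose samples all fall on Day 1, at 6.7% of a group per person. Exclusion of QD participants who stop on Days 2 to 6 depends on the undefined meaning of a pair. The rule can fall harder on QD than on BID or TID, because only the latter have a possible Day 1 route and their troughs come sooner after a dose.

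Loss through low troughs, including from the EC90 fit, is a conditional risk of unknown size. It rests on assumed half-lives, an assumed LLOQ relative to peak, first-order decline and a peak near 2 h. The primary efficacy and safety analyses are unaffected.

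**What to change.** In SAP Table 6, define the PK population as participants who received at least one dose of TBA-7371 and have at least one measurable post-dose concentration. This is in effect the protocol rule; the word post-dose is an addition, so state it in SAP section 8 with any other remaining difference from Protocol Table 8. Apply evaluability parameter by parameter, for example for half-life, where section 13.1 already sets criteria for the terminal slope.

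If a pair rule is kept, say whether the two samples must be from the same day and around the same dose, say whether the 12h and 7h samples count as pre-dose, let a pre-dose value below the quantification limit count, and declare the rule in section 8.

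The cost is one table cell and a sentence or two in section 8. No extra sampling is needed and no valid data are lost.

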8 CHANGES IN CONDUCT / RE-LANNED ANALYSES FROM THE PROTOCOL

No changes have been made to the planned analyses.

9 OVERALL STATISTICAL CONSIDERATIONS

9.1 General Conventions

Treatment groups consist of the following study interventions:

1. TBA-7371 100 mg QD
2. TBA-7371 100 mg BID
3. TBA-7371 200 mg QD
4. TBA-7371 100 mg TID
5. TBA-7371 400 mg QD
6. HRZE QD

The nomenclatures of study interventions will be used to display in tables, figures, and listings.

All measured variables and derived parameters will be listed individually and, if appropriate, tabulated using descriptive statistics. For categorical variables, summary tables will be provided giving sample size, absolute and relative frequency. For continuous variables, summary tables will be provided giving sample size, arithmetic mean, geometric mean (if appropriate), standard deviation, coefficient of variation (if appropriate), median, minimum and maximum. For variables with non-normal distribution, medians and interquartile range will be calculated, and the appropriate non-parametric tests will be applied. Unless specified otherwise, all confidence intervals will be two-sided 95% confidence intervals. Given the primary endpoint is tested using a one-sided test at 0.05, the corresponding 90% confidence interval will be provided. One-sided p-value will be displayed with 4 decimal places; if the p-value is less than 0.0001, display as “<0.0001”.

Change from baseline or screening for a measured variable at a particular post-baseline time point will be computed as the value at the post-baseline time point minus the baseline or screening value, as appropriate.

Percentages will be displayed with one decimal place and percentages for zero counts will be omitted from the presented results. If the percentage is greater than 0 but rounds to 0.0% (e.g. 0.04%), display as “(<0.1)”.

SAS code of SAS procedures that will be used to perform efficacy and safety analyses is provided in [Appendix 4](#).

9.2 Definitions

Screening EBA Measure: Average of the EBA measurements (i.e., log CFU, TTP in MGIT, and log concentration of sputum LAM) from the day -2 and day -1 overnight sputum samples of the screening phase will be used to determine the screening EBA measurement. If one of the overnight sputum samples is missing, the single non-missing sample will be directly used as the screening EBA measurement.

Baseline definition for other efficacy and safety variables: The last assessment made prior to the first administered dose of study intervention will be considered baseline for analysis purposes. Baseline values of ECG and vital signs are measured on Day 1 before the first dose of study medication is administered.

Day 1: Study day 1 is the day of first administration of TBA-7371 or HRZE. Positive study days will be counted forward from Day 1. Day -1 will be the date immediately preceding Day 1, and negative study days will be counted backward from Day 1.

9.3 Interim Analysis

No formal interim analysis is planned in this trial.

Unmasked safety and (if available) PK data on each cohort will be provided to the Independent Data Monitoring Committee (IDMC) to aid in recommendations related to dose escalation.

9.4 Handling of Missing Data

9.4.1 Missing or Partial Dates for Adverse Events

Missing or partial AE start dates will be imputed for the purpose of determining whether the AEs are treatment emergent. Data handling rules for missing or partial start/stop date for AEs are detailed in [Appendix 2](#). The missing or partial dates will be displayed in the data listings as reported on the electronic case report form (eCRF) rather than the imputed dates.

9.4.2 Missing Incomplete Dates for Prior or Concomitant Medications

Missing or partial medication start or stop dates will be imputed for the purpose of determining whether the medication are taken concomitantly. Data handling rules for missing or partial start/stop date medications are detailed in [Appendix 3](#). The missing or partial dates will be displayed in the data listings as reported on the eCRF rather than the imputed dates.

9.4.3 Missing Efficacy Data

Unless specified otherwise, no imputation for missing efficacy data will be performed for the planned efficacy analyses.

9.5 Independent Data Monitoring Committee (IDMC)

The IDMC is established to oversee the safety of this study and to make a go/no-go recommendation at each dose escalation step.

The IDMC will operate according to the most current version of the IDMC charter, outlined in the introduction section of this document. The IDMC structure, participants and other details are provided in the charter and are not repeated in this document. The charter describes the scope of responsibilities of the IDMC and identifies its members. Additionally, it outlines the meeting schedule and format, provides procedures for ensuring confidentiality, and explains the administrative procedures that will be followed. The IDMC charter provides meeting information and other details.

The IDMC will review patient profiles containing unmasked safety and, if available, PK data during regularly scheduled safety review meetings. The IDMC may request additional information, or a pause in recruitment and study treatment, while safety data are being evaluated.

9.6 Masking (Blinding)

This study will be open label for study participants, study site personnel, IDMC members, laboratory personnel involved in PK measurements and all sponsor and CRO personnel. The study will be masked (blinded) for personnel involved in the conduct of all other laboratory procedures (including those for the primary end-point).

9.7 Pooling Strategy for Study Sites

Data will be pooled across all study sites.

9.8 Visit Windows/Unscheduled Visits

Efficacy and safety analyses will use the nominal visits as collected in the study database, thereby, visit windows will not be applied.

Unscheduled visits will not be included in by-visit summaries or analysis, but may contribute to the baseline value and worst post-baseline assessments.

10 STATISTICAL ANALYSIS METHODS

10.1 Participant Disposition

The number and percentages of participants for each population (m' T, PP, Safety, and PK) will be summarized. For computing percentages, the denominator will be the number of participants in the mITT population.

Participants' disposition will be summarized for the following study phases:

Screening Phase:

The numbers and percentages of participants who were screened, screen failures, and reasons for screen failure. For computing percentages, the denominator will be the number of participants screened.

Study Treatment Phase:

The number and percentages of participants who were randomized, completed treatment, discontinued treatment and reasons for discontinuation of treatment, completed study, discontinued study and reasons for discontinuation of study will be tabulated by treatment group and will be summarized for mITT PP, Safety and PK populations. For computing percentages, the denominator will be the number of participants for the given population and treatment group.

